2. INTRODUCTION

2.1 Insertional-non-insertional-mixed yarrow tendinopathy

Achilles tendinopathy is a condition characterized by inflammation of the Achilles tendon. The latter is the largest tendon in the human body, is about 15 cm long, and originates from the triceps muscle of the sura, formed by the twin muscles, whose tendon fibers insert postero-laterally to the calcaneal bone, and the soleus, whose tendon fibers insert antero-medially to the calcaneal bone, giving rise precisely to the Achilles tendon.

Two types of forces act on the Achilles tendon: one exerted by the tendons of the gastrocnemius and soleus muscles, and one resulting from the compressive action of the calcaneal bone on the tendon. In case of excessive mechanical stress by these two forces, the tendon undergoes degeneration triggering tendinopathy [1].

Approximately 6% of the general population suffers from achilles tendinopathy during their lifetime [2]. Achilles tendinopathies are classified into insertional tendinitis and noninsertional tendinitis. Insertional tendinitis involves the lower part of the tendon, where the tendon inserts at the level of the calcaneus, and can affect even patients who are not particularly athletically active [3].

Noninsertional tendinitis occurs when the fibers in the middle portion of the tendon are affected, affects young and athletic people the most and has a high incidence (30-50%) in middle-aged individuals. Such pathology in the young and athletic patient often requires a complete cessation of physical activities for long periods of time and may go so far as to interfere with work activities, thus in fact constituting a significant social cost, as well as a highly disabling and impacting factor on the patient's quality of life.

Clinically, patients present with reduced dorsiflexion and plantarflexion deficits with acupressure tenderness in the insertional and noninsertional sites of the affected achilles region. On inspection of the posterior calcaneal portion, patients may present with an erythematous and mildly edematous area associated with an initial picture of swelling at the achilles site. Patients also report pain aggravated by exercise (running, jumping, walking).

Regarding diagnosis, in the first instance, it is advisable to perform a standard loaded radiograph of the foot to visualize any enthesopathy and peri- and intra-tendinous calcifications. It is also advisable to perform a musculoskeletal ultrasonography and as a second-level investigation an MRI, in order to visualize optimally the soft tissues and thus a tendon degeneration, although signs of tendon degeneration are not always accompanied by a positive clinical picture, either in the acute or subacute phase.

We can distinguish conservative and nonconservative treatments.

Conservative treatments include: exercise in an eccentric regimen as recommended by the 2010 "American Physical Therapy Association" guidelines (Grade A) [4]; focused shock wave physical therapy as suggested by the recent study by "Chimenti et al. " of 2017 (Grade B) [1]; the use of nocturnal splints,

on the other hand, does not present sufficient evidence to justify their use; corticosteroid and platelet-rich plasma (PRP) infiltrations, although frequently used in clinical practice, are not supported by solid scientific evidence.

In the literature, by contrast, we recall the 2012 study by Monto RR. who reports the satisfaction of 28 out of 30 patients with achilles tendinopathy treated with PRP ^[5] and several other Authors who have gained experience in this regard ^[6;7;8;9;10;11]. The use of SVF adipose stromal fraction in the treatment of tendinopathies is still being studied ^[12;13].

Non-conservative treatments include various surgical approaches, which may involve more complex tendon transfer surgeries, such as transposition of the long flexor hallux, or simpler scarification approaches; minimally invasive endoscopic approaches; or percutaneous echo-guided procedures, all of which currently lack sufficient scientific support.

Conservative treatment alone is often found to be unsatisfactory in 40% of cases, while proposed traditional and minimally invasive surgical treatments (such as scarifications) have mixed results and are not always reproducible in the literature.

In light of this, there appears to be a clear need to find minimally invasive therapeutic alternatives that can guarantee to achieve better results than the current ones in the early treatment of acute and subacute insertional and noninsertional achilles tendinopathies.

2.2 Role of collagen in the pathogenesis of Achilles tendinopathy

Recently, a line of medical devices based on collagen and ancillary substances has been produced by Guna S.p.a., including MD-Tissue Collagen Medical Device. Collagen is the most abundant protein in mammals, accounting for about 5 to 6 % of an adult human's body weight. A third to a quarter of all protein mass in higher animals is collagen: from bones to tendons, joint capsules to muscles, ligaments to fasciae, teeth to serosae, and skin to extracellular matrix (ECM). It is found in most tissues, and particularly in those tissues that require both flexibility and strength such as skin, tendons, and muscle fascias. There are 14 types of collagen, the most represented type being type I. In humans, the peak of collagen biosynthesis occurs from age 45 to 60. Thereafter, its production drops very rapidly, along with that of elastin and proteoglycans. The unit-base of collagen is tropocollagen, a glycoprotein formed by the intertwining of three left-handed polypeptide chains carrying glucose and galactose molecules, attached only to the amino acid molecule Hydroxylysine (Hyl), one of only four amino acids constituting tropo-collagen with Glycine (Gly), Proline (Pro) and 4-Hydroxyproline (Hyp). This tight triple helix provides the structural strength and rigidity, but also the strength and flexibility necessary for perfect collagen function. The arrangement of fibrils in the formation of collagen fibers, provides the structure with great robustness in terms of strength, inextensibility, incompressibility, but also plasticity, flexibility, resistance to loading, and resistance to twisting. Due to its abundance in nature (more than 90 % of fibrous proteins are made up of type I collagen) and its unique physical and

biological properties, type I collagen has been used extensively to produce medical devices, and among these are the injectable medical devices produced by Guna S.p.a. called Collagen Medical Devices based on porcine collagen. In orthopedics and traumatology and in rehabilitation medicine, this evidence on the structural role of collagen holds particular importance since all extra- and intra-articular structures are basically made up of this molecule [14;15;16].

2.3. Collagen in the therapy of achilles tendinopathy

In view of the morpho-structural changes that characterize Achilles tendinopathy, the use of injectable medical devices such as Collagen Medical Devices might find therapeutic indication. For some years now, in fact, the use of injectable medical devices based on porcine collagen and ancillary substances of natural origin (*Collagen Medical Devices GUNA*) has been introduced in the treatment of painful and degenerative pathologies of the locomotor system, which allow a more effective and specific placement of collagen in situ with the function of vehiculation and stabilization. The collagen used in Collagen Medical Devices GUNA undergoes a special process of tangential filtration, sterilization, and molecular weight control, resulting in a pure product. Infiltrative therapy based on *Collagen Medical Devices* would make it possible to replace, reinforce, structure and protect (adhesion barrier) cartilage, tendons, ligaments, joint capsules, etc., improving the arrangement of collagen fibers and all the anatomical structures in which it is present and, at the same time, provide mechanical type support to the affected district.

In particular, MD-Tissue *Collagen Medical Device* could play a positive role in the treatment of Achilles tendon pathology.

3. SCIENTIFIC REQUIREMENTS

3.1. Title of the research

Evaluation of collagen-based medical device treatment combined with physiotherapy in subjects with achilles tendinopathy. Multicenter randomized clinical investigation; AKITENMED STUDY.

3.2. Purpose of research

Considering that there are no strong evidence-based guidelines in the area of treatment of achilles tendinopathy, the purpose of this research project is to understand through a multicenter, randomized clinical investigation the impact of treatment with a porcine collagen-based medical device administered in the peri-tendon area in combination with physiotherapy on pain reduction and functional improvement of the investigated tendon.

3.3. Design of the clinical investigation

The multicenter, randomized clinical investigation is prospective, and will have a total duration of 8 weeks.

After enrollment, subjects will be randomized and assigned to two experimental groups:

- **Group A** which, alongside physiotherapy (eccentric strengthening protocol) will receive MD-Tissue Collagen Medical Device.
- **Group B** which, will implement only physiotherapy (eccentric strengthening protocol).

Variables will be assessed at baseline (T0 time), after 1 week (T1w), after 2 weeks (T2w), after 3 weeks (T3w), or at the end of injection treatment, and after 6 weeks after enrollment (T6w/FU). Further evaluation will be carried out after 2 weeks, or after 8 weeks (T8w/FU) from the start of the clinical investigation.

After enrollment, subjects in both groups will begin a 6-week physiotherapy course (eccentric strengthening protocol). Each session will consist of Achilles tendon stretching exercises. See § 3.12.

3.4. Duration of the clinical study

The clinical study will last for 8 weeks (see Figure 1). A subject selection and recruitment period of 8 months is expected. The total duration of the clinical study will be 10 months.

[figure not shown]

Fig.1 Study design flow chart

3.5. Participant population

A total of 72 subjects with achilles tendinopathy will be enrolled. The recruitment phase will be closed no sooner than the number of subjects in the clinical investigation plan has been reached.

Only subjects will be included in the two experimental groups:

- belonging to the departments of the experimental centers;
- who meet the inclusion criteria and have no exclusion criteria.

3.6. Inclusion Criteria

- Male and female subjects aged 18 to 70 years.
- Subjects with tendon pain for not more than 24 weeks;
- Subjects with clinically diagnosed and ultrasonographically confirmed. insertional/noninsertional/mystic tendinopathy;
- Subjects with a VISA A score between 50 and 75;
- VAS \geq 5;
- Subjects able to understand and answer the SF12 questionnaire.
- Subjects able to understand and sign the informed consent.

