4.15. Plan of statistical analysis

The primary endpoint will be evaluated by Ancova, as described in the numerosity calculation.

Secondary endpoints will be assessed as follows: 1) the VISA-A score at time T3s and T6s/FU compared with time T0 with Anova at repeated measures between group and within group; 2) the VAS at time T3s, T6s/FU and T8s/FU compared with time T0 with Anova at repeated measures between group and within group; 3) the SF12 questionnaire at time T3s, T6s/FU and T8s/FU compared with time T0 with Anova at repeated measures or Friedman's test; 4) the fraction of subjects in each group reaching Minimal Clinical Disease (MCD) considering that the MCD of the VISA-A questionnaire is 18.5 (90% MCD) with Fisher's exact test; 5) the units of analgesic drug consumed according to the clinical diary at time T3s, T6s/FUs and time T8s/FUs (paracetamol 1000 mg will be used as "rescue dose" in case of pain onset/recrudescence) with Friedman's exact test; 6) the fraction of subjects in each group who drop out of the investigation early in relation to Adverse Events (AE/SAE/SUSAR) with Fisher's exact test.

Statistical significance will be assumed for $p < 0.05$, unless corrected for multiple testing.

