### 3.5. Participant population

A total of 72 subjects with achilles tendinopathy will be enrolled. The recruitment phase will be closed no sooner than the number of subjects in the clinical investigation plan has been reached.

Only subjects will be included in the two experimental groups:

- belonging to the departments of the experimental centers;
- who meet the inclusion criteria and have no exclusion criteria.

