### 3.6. Inclusion Criteria

- Male and female subjects aged 18 to 60 years;
- Subjects with tendon pain for not more than 6 weeks;
- Subjects with clinically diagnosed and ultrasonographically confirmed insertional/noninsertional/mystic tendinopathy;
- Subjects with a VISA A score between 50 and 75;
- VAS  $\geq$  5;
- Subjects able to understand and answer the SF12 questionnaire;
- Subjects able to understand and sign the informed consent.

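### Do the two different sets of entry limits in Section 3.6 leave it open who is in the primary analysis?

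*Protocol*

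**What the plan says.** The two documents are full texts of the same plan, and their Sections 3.6 differ in two of seven inclusion criteria.

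- Age: "Male and female subjects aged 18 to 70 years" in the Protocol; "Male and female subjects aged 18 to 60 years" in the Combined protocol and SAP.
- Symptom duration: "Subjects with tendon pain for not more than 24 weeks" in the Protocol; "Subjects with tendon pain for not more than 6 weeks" in the Combined protocol and SAP.

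The other five inclusion criteria and all 15 exclusion criteria in Section 3.7 agree. Section 3.5 is the same in both. It sets the size ("A total of 72 subjects with achilles tendinopathy will be enrolled") and the entry rule ("Only subjects will be included in the two experimental groups"), namely those from the participating departments "who meet the inclusion criteria and have no exclusion criteria".

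Section 4.14 (sample size) has the same content in both. So does Section 4.15, which says of the primary analysis: "The primary endpoint will be evaluated by Ancova, as described in the numerosity calculation". Neither text defines an intention-to-treat, full-analysis or per-protocol set. Neither has a rule for subjects enrolled under different limits.

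**The concern.** The longest permitted pain duration differs fourfold (24 against 6 weeks) and the upper age limit by ten years. If both sets of limits were used in sequence, a randomised subject aged 61 to 70, or with more than 6 and up to 24 weeks of pain, qualifies under one text and not under the other. Someone could then argue from Section 3.5 that this subject does not belong to the groups, and Section 4.15 does not answer the argument.

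An open choice matters more in this trial than in a blinded one. One arm receives six injections and the other none, and under Section 3.8 each Principal Investigator and the sponsor's research unit hold the randomisation list. If the choice between all randomised subjects and only those within the narrower limits were made after seeing results, the primary endpoint would in effect be tested twice at 0.05. Readers would also not know to whom the result applies.

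**Working it through.** **1. Compare the criteria.**

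| Item | Protocol | Combined protocol and SAP |
|---|---|---|
| Age | 18–70 | 18–60 |
| Pain duration | up to 24 weeks | up to 6 weeks |
| Other five inclusion criteria | same | same |
| 15 exclusion criteria | same | same |
| Sections 4.14 and 4.15 | same | same |

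The limits are nested: everyone who meets the narrower set meets the wider one.

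**2. Reproduce the plan's own figure.** Inputs from Section 4.14: 28 per arm, difference 12, SD 15, R² 0.2, F-test at 0.05.

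- Residual variance = 15² × (1 − 0.2) = 180.
- Noncentrality = (12² / 180) × 28 / 2 = 0.8 × 14 = 11.2.
- Noncentral F with 1 and 53 degrees of freedom gives power 90.75%, as stated.

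This figure is for 28 analysed per arm. The 36 per arm to be randomised allow for 20% dropout (28 / 0.8 = 35; the plan states 36). It should not be read as the power with all 36 analysed.

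**3. Work through the possible histories.**

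- *Only one set of limits was ever used.* Every properly enrolled subject meets it, and the analysis is unaffected.
- *Wider limits first, then narrower.* Subjects enrolled early met the text then in force. The later text governs later entries.
- *Narrower limits first, then wider.* Early subjects meet both sets. Later subjects meet the text then in force.

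In each case every properly enrolled subject satisfied Section 3.5 on the day of entry. That section says who may enter the groups and is silent on who is analysed. Section 3.15 lists the reasons for leaving early (own request, investigator's discretion, adverse event). These concern leaving the study, not removal from the analysis because of another version's limits. The section also asks for a final evaluation of those who leave, unless they decline. Subjects therefore stay in the arm assigned unless someone adds a rule that the plan does not contain. Because allocation is random whatever the limits, that comparison is valid under either set.

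**4. Size of the feared problem, if someone did choose afterwards.** The full-set and nested-subset statistics correlate at √(share within the narrower limits). The chance under no effect that either |z| exceeds 1.96 is:

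| Share within narrower limits (assumed) | Correlation | Chance of a false positive |
|---|---|---|
| 75% | 0.866 | 7.3% |
| 50% | 0.707 | 8.3% |
| 25% | 0.500 | 9.1% |

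The documents give no shares. The figures also need four conditions together: both limits applied; subjects outside the narrower limits were enrolled; the set was chosen after seeing results; and success was claimed if either test passed.

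**5. What restriction would cost.** With the same effect, SD and R², cutting the analysed number from 28 to 21 per arm (25% dropped) lowers power from 90.75% to 80.7%, and cutting it to 14 (50% dropped) lowers it to 62.4%. The design gives no reason to prefer the narrower subset as the primary set.

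**The case for a change.** The best case for acting is that dating the versions would not by itself settle the analysis. Section 4.15 would still name no analysis set, allocation is visible, and Section 3.5 gives a textual foothold to anyone wishing to drop a 65-year-old or a subject with 12 weeks of pain. One added sentence would close the door at almost no cost.

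Much of this is accurate. The difference between the texts is real, the analysis set is unnamed, and the error rates in the working are correct for the situation they describe. Readers should also be told how many subjects per arm entered under each set, if both were used.

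Three things limit it. First, the trigger is not established: the title pages that could carry version and date are not available to this review, and different eligibility in two versions is not in itself an error. Second, the foothold is weak, because an entry rule read as a retrospective exclusion is not what Section 3.5 says. Third, the unnamed analysis set would be just as unnamed with a single version; it does not arise from Section 3.6. Nor is one sentence a full remedy: a statement that all randomised subjects are analysed cannot be carried out for subjects without a week-8 VISA-A score unless a rule for missing scores goes with it. That is a matter of general documentation, separate from the entry limits.

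**Conclusion.** No change to the plan follows. The discrepancy in Section 3.6 is real, but its effect on the primary comparison is nil if one set of limits always applied. It is also nil if both applied in sequence and subjects are analysed in the arm assigned, which is the default that the texts leave in place. The 7.3% to 9.1% range is not an estimate for this trial; it rests on assumed shares and on a post hoc choice that no section plans or hints at. No stated rule gives a wrong result, and no stated method would be replaced by a better one.

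The two passages should be reconciled as a matter of record, or the sponsor should state which limits applied and from what date. If both applied, the report should give the number randomised per arm under each. The conclusion assumes that subjects were enrolled under the text in force on the day and that nobody is later excluded by reference to the other text. No view is taken on which limits are right.

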3.14. Criteria of effectiveness

3.14.1 Primary Endpoint

The primary end point will be assessed at T8s/FU and will involve:

- Assessment of the VISA-A questionnaire score at time T8w/FU compared to time T0. A difference between the two groups of 12 out of 100 points on the questionnaire can be considered clinically significant [17].

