4. STATISTICS

4.14. Sample size

A one-covariance analysis for two arms of 28 subjects each, in which the covariate of interest differs by 12 units in its mean value between the two arms (compared with a null hypothesis of no difference), with a common standard deviation assumed to be 15 units, and an R^2 value assumed to be 0.2 has a

power of 90.75% in discriminating the established difference between mean values, using an F-test at a significance level of 0.05.

Assuming dropout patients to be 20% of the total, the inflated sample size of the protocol becomes 36 patients per arm.

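### Under the Protocol's 24-week limit, pain duration is known at T0 but no analysis uses it; adding it to the primary ANCOVA is a small, optional precision gain

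*Protocol*

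**What the plan says.** Section 3.6 of the Protocol sets an upper limit on symptom duration and no lower one: "Subjects with tendon pain for not more than 24 weeks". The same section of the Combined protocol and SAP reads "Subjects with tendon pain for not more than 6 weeks". The text provided does not say which governs.

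The introduction (2.1) places the clinical need in the "early treatment of acute and subacute insertional and noninsertional achilles tendinopathies" and gives neither term a cut-off in weeks. The formal purpose (3.2) is the effect of the device "in combination with physiotherapy on pain reduction and functional improvement of the investigated tendon", with no restriction to early disease.

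The primary endpoint (3.14.1) is "Assessment of the VISA-A questionnaire score at time T8w/FU compared to time T0". For its analysis, 4.15 says: "The primary endpoint will be evaluated by Ancova, as described in the numerosity calculation". Section 4.14 describes "A one-covariance analysis for two arms of 28 subjects each", with a difference of 12, SD 15, R² 0.2 and power 90.75%. It does not clearly name the single covariate; T0 VISA-A is the natural reading, since the endpoint compares T8 with T0.

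Randomisation (3.8) is blocked within centre. Duration does not appear there, and none of the analyses in 4.15 uses it.

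**The concern.** With a 24-week limit, a subject in the first days of pain and one with more than five months of pain can both be enrolled. If recovery over 8 weeks depends on time since onset, that variation stays in the residual of the primary test and the interval for the A–B difference is wider than it need be. The information is available without extra visits: duration has to be established to check eligibility, and Table 1 schedules a medical history at T0. What is at stake is some precision. The validity of the comparison is not in question.

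**Working it through.** **Inputs from 4.14:** 28 evaluable per arm, difference 12, SD 15, R² 0.2, F-test at 0.05. **Assumed, because no document gives it:** r, the share of the variance left after the planned covariate that duration would explain, taken as 0, 2, 5 and 10%.

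**Step 1. Reproduce the plan's figure.** Residual variance = 15² × (1 − 0.2) = 180. Noncentrality = (28/2) × 12²/180 = 11.2. Residual df = 56 − 3 = 53. Power from the noncentral F is 0.9075, which matches the stated 90.75%. SE of the A–B difference = √(180 × 2/28) = 3.586; 95% CI half-width = 2.006 × 3.586 = 7.19 points.

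**Step 2. Add duration as a second covariate.** Residual variance = 180 × (1 − r); residual df = 52.

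| r (assumed) | Residual variance | SE | Power | 95% CI half-width |
|---|---|---|---|---|
| planned model | 180 | 3.586 | 90.75% | 7.19 |
| 0 | 180 | 3.586 | 90.73% | 7.20 |
| 0.02 | 176.4 | 3.550 | 91.27% | 7.12 |
| 0.05 | 171 | 3.495 | 92.07% | 7.01 |
| 0.10 | 162 | 3.402 | 93.34% | 6.83 |

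If the share is instead taken of total variance, so that residual variance is 225 × (0.8 − x), power at 2, 5 and 10% is 91.4, 92.4 and 94.0%. The message is the same.

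Like the plan's own calculation, the table treats covariates as balanced between arms. With 56 subjects and a roughly normal covariate, chance correlation with arm inflates the adjusted variance on average by (56 − 4)/(56 − 5) = 52/51, about 2%. Since 0.98 × 52/51 is almost exactly 1, r = 0.02 is close to break-even, and a clear gain needs a larger r.

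**Step 3. Check whether chance imbalance in duration is a separate gain.** At r = 0.10, the part of the A–B difference due to imbalance has SD √(0.10 × 180 × 2/28) = 1.134, or 1.96 × 1.134 = 2.22 points. Its variance, 1.134² = 1.286, equals the drop in squared SE in the table: 12.857 − 11.571 = 1.286. It is the same quantity and must not be counted again.

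**Step 4. What an arm-by-duration term could show.** Split the 28 per arm into m with shorter and 28 − m with longer duration. The interaction SE is √(180 × (2/m + 2/(28 − m))). With an assumed 25, 50 or 75% of shorter duration (m = 7, 14, 21), the SE is 8.28, 7.17 or 8.28, and power (normal approximation) for a 12-point difference in effect is about 31, 39 or 31%.

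**The case against.** The strongest reply is that little depends on this. Planned power already exceeds 90%, the assumed gain is at most about 2.6 power points (93.34 − 90.75), and the half-width narrows by at most 0.36 points (7.19 − 6.83). No passage says that duration predicts T8 VISA-A, and the same arithmetic would apply to any other baseline variable. All of this stands, and it is why the point is optional. What remains specific to duration is that it is an eligibility variable in this trial, must be established at T0, and bears on the rationale in 2.1.

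The second reply is that the premise depends on which text governs. This also stands. Under the 6-week limit in the Combined protocol and SAP most of the spread disappears.

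A reader might infer more: that the trial leaves the early-disease question unanswered. The documents do not support this. Section 3.2 sets no early-disease aim, acute and subacute are not defined in weeks, and the average effect in the admitted population includes early disease. All that can be said is that no estimate by duration is planned, and Step 4 shows that one would be imprecise.

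**Conclusion.** The point holds as a minor one, conditional on the Protocol's 24-week text governing. Duration is established at T0 and then not used. Prespecifying it as a covariate would move power from 90.75% to between 90.73% and 93.34%, and the half-width from 7.19 to between 7.20 and 6.83 points, for an assumed r of 0 to 10%. The true r is not in the documents and may be zero.

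Two stronger readings should be resisted. A reader might infer that omitting duration biases the T8 contrast; randomisation rules that out. A reader might also infer that the trial is underpowered; the stated 90.75% reproduces without duration in the model.

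**What to change.** - In 4.15, name the terms of the primary ANCOVA in advance: arm, T0 VISA-A (after confirming that this is the covariate meant in 4.14) and continuous pain duration at T0. Fix the scale for duration at the same time. Adding it only after an imbalance has been seen would be a data-driven choice.
- Confirm that the T0 data collection form, which is not among the documents, holds duration as a number of weeks.
- If an arm-by-duration estimate is reported, give it with its 95% CI and label it exploratory, noting the power of about 31–39%.
- Reconcile the 24-week and 6-week limits in the two versions of 3.6. This point takes no position on which is right.

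The cost is one sentence in 4.15, at most one numeric field, and one residual degree of freedom (90.75% to 90.73% if duration explains nothing), plus the roughly 2% average variance inflation noted above. No additional subjects or visits are needed.
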